3.6. Study Variables

Clinical and Demographic Information

Clinical and demographic information will be obtained by personal interview and, if necessary, review of medical records. This information will include a complete medical history, including demographic information, with specific emphasis on bone-related issues (history of fracture, endocrinopathy, vitamin D intake, etc.) utilizing a bone health questionnaire used by our group to acquire baseline data for our in-house bone registry (Spinal Cord Injury & Lifestyle Information Form). They will also complete the Spinal Cord Independence Measure^{77,78} (SCIM) prior to randomization. In order to assess ambulatory ability and status, participants will be asked to complete the Walking Index for Spinal Cord Injury⁷⁹ at each visit. This is a validated instrument to assess activity levels that affect bone loading and may be expected to have an impact on the effects of treatment that participants will be receiving.

DXA BMD

BMD will be determined by DXA at various skeletal sites (bilateral total hip, bilateral femoral neck, spine, non-dominant forearm, non-dominant knee (distal femur, proximal tibia), total body). The DXA scans will be performed at Baseline, 3 mos, 6 mos, 12 mos, 18 mos, and 24 mos by a trained DXA technician from our study team using a Hologic QDR 4500A densitometer. DXA scans performed at SRAlab will be done on the Hologic Horizon DXA scanner and will be performed by a SRAlab DXA technician, with oversight by our study team. All subjects who have their baseline scan at SRAlab will continue their follow up on the same machine. Whole body and forearm scans will be optional scans as they do not contribute to the primary or secondary study endpoints. Standard acquisition and analysis protocols will be used to quantify areal bone mineral density (aBMD) of all skeletal sites.

We have had extensive experience in DXA imaging of individuals with SCI. There have been no technical problems with DXA imaging though positioning has been challenging for some participants due to contractures and spasticity, and orthopedic hardware has also prevented the full set of images from being obtained. For those individuals with obstacles in obtaining images of the non-dominant knee and/or forearm, the dominant extremity will be used. As much as possible, positioning is reproduced at subsequent visits to allow appropriate comparisons.

CT determined bone parameters.

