Excessive Bone Loss: Participants receiving placebo may experience significant bone loss during the course of the study. Although the current standard of care in acute SCI is to not treat individuals, in this study where treatment is an option, it is not felt to be ethical to withhold treatment from individuals who have experienced extensive bone loss that would put them at risk for the development of osteoporosis. Whether such treatment in this setting would be effective is unknown, and the focus of this study, but participants should have the benefit of making an informed decision regarding their wish for intervention. It is acknowledged that this decision may be controversial, but it is felt to be in the best interests of the participants and has been supported on review by both the FDA and our institutional review board. Therefore, during this study, individuals who experience a loss of 20% or more of bone mass from baseline, detected on at least two sites on repeat testing at the 6 month study visit, will be offered the opportunity to be treated with whatever medication they did not receive at their baseline visit. The participants and the research team will continue to be blinded to study treatment; the decision regarding treatment allocation will be made by the unblinded pharmacist. These participants will be followed for additional 18 months according to the study schedule, but will not be re-randomized at the one year visit. All participants will continue to be followed in the study, regardless of whether they choose to be retreated or not, and all efforts will be made to collect data through 2 full years of follow-up. For those individuals who reach this safety cut-off, all further data will be censored at that point for the purposes of data analysis.

Zoledronic acid: The most serious risks associated with the infusion of zoledronic acid are the possibility of acute renal failure and hypocalcemia. Other risks associated with zoledronic acid, seen also with other bisphosphonates, include osteonecrosis of the jaw and the possibility of severe bone, joint and muscle pains. The most common adverse reactions (greater than 10%) reported with the use of zoledronic acid are pyrexia, myalgia, headache, arthralgia, and pain in extremity. Other important adverse reactions were flu-like illness, nausea, vomiting, diarrhea,

and eye inflammation. An acute flu-like response is seen in greater than 10% of people within 24 hours of infusion.

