14.1. Overview

Please refer to document titled, "Statistical Analysis Plan version 2.2, dated 17Jun2020," which supersedes the analysis plan described in this section.

The main goal of the analytic strategy is to determine whether active treatment versus placebo influences the trajectory of change over time in bone density. This is a clinical trial, so we

will use an endpoint analysis as the primary means to determine whether treatment has been effective. The primary dependent variable will be change in BMD from baseline. The primary dependent variable will be change in BMD from baseline. We will retain all cases in the analysis using an intent-to-treat methodology. In order to ensure that treatment efficacy is not overestimated by participants who worsen dropping out of treatment, we will use the last-observation- carried-forward (LOCF) methodology to impute any data that are missing at the end of treatment. We understand that this method has limitations and may be overly conservative, but we will also have the ability to employ growth curve modeling, which can describe change over time even when some data are missing, and when assessment timing is different across participants. We plan to study 30 participants in each group (overall $N = 60$).

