## Endpoints

**Primary endpoints.** The primary endpoints in this study are the percent-change in aBMD, evaluated by DXA, in the non-dominant (1) total hip and (2) femoral neck skeletal sites. If data on the non-dominant hip are unavailable, we will use aBMD for the dominant hip. Percent-change will be calculated as  $((\text{aBMD}_{\text{follow-up}} - \text{aBMD}_{\text{baseline}}) / \text{aBMD}_{\text{baseline}}) \times 100\%$ .

**Key secondary endpoints.** Secondary endpoints include: (1) integral volumetric bone mineral content (Int.vBMC) distal femoral epiphysis, (2) Int. vBMC tibial epiphysis, and (3) Int.vBMC distal femoral metaphysis measured by QCT. Percent-change will again be calculated for each outcome.

**Additional secondary endpoints.** CT biomarkers: Trabecular volumetric bone mineral density (Tb.vBMD; g/cm^3) and cortical volumetric bone mineral content (Ct.vBMC; g) and bone volume (Ct.vBV; cm^3) at epiphyseal and metaphyseal regions. For the diaphyseal region, Ct.vBMC and Ct.vBV. WISCI.

**Exploratory endpoints.** Torsional strength index (TSI; cm^3) for each skeletal region. Stiffness and strength at the hip, distal femur, and proximal tibia determined by CT-based finite element analysis. Serum markers of bone metabolism: P1NP, BSAP (bone formation markers), and CTX (bone resorption marker).

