## Statistical Methods

### *Diagnostics*

All variables will be plotted to examine distribution shapes as well as percentage of missing values. The mixed modelling proposed below uses both all available observations without deleting cases and imputed data. Residuals will be examined for each model fitted in case of unexpected violations of assumptions. Analysis will be performed as ITT (intention to treat): patients will be analyzed according to the treatment arm to which they were randomized.

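### The protocol censors everyone who reaches the month-6 bone-loss cut-off, including those who decline the infusion; the SAP's intention-to-treat rule is not reconciled with this

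*Protocol*

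**What the plan says.** The rule is in the Excessive Bone Loss paragraph of protocol Section 10. The cut-off is a loss of at least 20% from baseline, "detected on at least two sites on repeat testing at the 6 month study visit". Those who meet it may choose a blinded infusion of the treatment they did not receive at baseline. Two statements about follow-up come next: these participants stay on the visit schedule "but will not be re-randomized at the one year visit", and "All participants will continue to be followed in the study, regardless of whether they choose to be retreated or not". The paragraph closes with the analysis rule: "For those individuals who reach this safety cut-off, all further data will be censored at that point for the purposes of data analysis".

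The qualifying sites are not listed. Section 3.6 gives the DXA sites as "bilateral total hip, bilateral femoral neck, spine, non-dominant forearm, non-dominant knee (distal femur, proximal tibia), total body".

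The SAP (Diagnostics) analyses patients by randomised arm and says that its mixed model "uses both all available observations without deleting cases". The primary endpoints are percent change in aBMD "in the non-dominant (1) total hip and (2) femoral neck skeletal sites", modelled at months 6 and 12 and tested in that order. Missing data are handled primarily by maximum likelihood. A later sensitivity analysis draws missing values around the participant's last observation.

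No part of the SAP mentions the cut-off, the month-6 infusion or censoring. Protocol Section 14.1 refers to the SAP as the document "which supersedes the analysis plan described in this section", which means Section 14. The Section 10 rule is neither withdrawn nor carried over.

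**The concern.** A participant who reaches the cut-off and declines the infusion has had nothing but the randomised treatment up to month 12. The month-12 DXA is scheduled and, under Section 10, still collected. If Section 10 is followed, that valid value is discarded because of a poor month-6 result. The loss depends on outcome and probably falls more often on placebo, so it would tend to shrink the month-12 difference.

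Decliners are to be expected. In the pilot study (Section 1.2), every placebo participant passed a 10% threshold and was offered retreatment, and 3 consented.

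Two analysts, one following Section 10 and the other the SAP, would build different month-12 datasets. At stake are the size of the estimate and what it estimates.

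**Working it through.** **1. The texts side by side.** For a decliner's month-12 hip value, Section 10 says exclude and the SAP says use what is available under the randomised arm. Nothing says whether a censored value counts as available. The SAP's precedence stops at Section 14, so it does not settle the matter.

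**2. The plan's own figure, and whether power is the issue.** Section 14.3 claims 80% power with 30 per group for d = 0.74, or for 6.5 points with SD 9.02. With two-sided alpha 0.05 (sidedness is not stated), d = 0.74 gives 81.8% (normal) or 80.5% (t), and 6.5/9.02 gives 79.7% or 78.4%. The claim reproduces. Now suppose half the placebo arm lost month 12 and nothing were recovered from month 6. With SD 9.02 the standard error is 9.02 × √(1/30 + 1/15) = 2.85. The smaller Table 2 total-hip difference is 13.83 − 3.40 = 10.43. Power is Φ(10.43/2.85 − 1.96), about 95%. Power is not the problem.

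**3. Who could reach the cut-off.** The documents give no month-6 data. As a guide, take P(loss ≥ 20%) = Φ((−20 − mean)/SD) from the 12-month means and SDs in Table 2, assuming normality:

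| Site | Placebo | Zoledronic acid |
|---|---|---|
| Left total hip | 0.1% | under 1% |
| Right total hip | 23% | under 1% |
| Left femoral neck | 24% | under 1% |
| Right femoral neck | 27% | under 1% |
| Left distal femur | 68% | 23% |

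For example, placebo right total hip is Φ((−20 + 18.21)/2.39) = Φ(−0.75) = 23%. Month-6 rates are probably lower. The knee is the likeliest trigger, and placebo is hit more often but not alone.

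**4. Bias in the month-12 total-hip difference.** By simulation, with these assumptions:
- Sites: both total hips, both femoral necks, distal femur and proximal tibia, with Table 2 distal femur values used for both knee sites.
- Month-6 mean 60% or 80% of the month-12 mean; month-6 SD equal to the month-12 SD or scaled by the same fraction.
- Between-site correlation 0.3 or 0.6, within-site correlation over time 0.7 or 0.9, from a shared patient factor plus site effect plus noise.
- Trigger: two or more sites at −20% or lower at month 6. All who trigger decline and lose month 12 (the upper case).
- Likelihood analysis: month 12 given the same hip's month 6, unstructured within arm.
- Imputation: censored values centred on month 6.

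That is 16 settings, each read for the left and right hip. Bias toward no effect, in percentage points:

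| Case | Likelihood (primary) | Imputation (sensitivity) |
|---|---|---|
| Table 2 SDs, knee counted | 0.00–0.23 (median 0.04) | 0.81–1.71 (median 1.17) |
| Table 2 SDs, hip sites only | at most 0.02 | at most 0.08 |
| Stress: hip SD 9.02, knee counted | 0.10–1.73 | 1.33–2.58 |
| Stress: hip SD 9.02, hip sites only | 0.01–0.90 | 0.16–1.07 |

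With Table 2 SDs and the knee counted, 14–40% of placebo and 2–12% of zoledronic acid participants trigger. With hip sites only, 0–2% of placebo do.

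**5. Hand check of the imputation column.** If 60–80% of the hip loss has occurred by month 6, the remaining loss is 20–40% of 13.83–18.21, or 2.8 to 7.3 points. Each 10% of placebo censored and frozen at month 6 then costs 0.10 × 2.8 to 0.10 × 7.3 = 0.28 to 0.73 point, the same order as the simulation.

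**6. Scaling to decliners.** The pilot had 14 participants, 7 on zoledronic acid, hence 7 on placebo. With 3 consenting, 4 of 7 declined, though at a 10% cut-off. Applying 4/7 to the first row of the table in step 4 gives about 0–0.13 point (likelihood) and 0.5–1.0 (imputation).

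**The case against.** The strongest reply is that the SAP governs the analysis, keeps all available observations, and so loses nothing. That is a possible reading, and a reader should not infer that month-12 data will certainly be removed. But the SAP's precedence is limited to Section 14 and it is silent on the cut-off, so the opposite reading is equally open. The conflict is established; the loss is conditional on following Section 10.

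A second reply is that the likelihood model keeps the month-6 hip value and so corrects the bias. Largely, it does. The cut-off needs two sites and each primary model holds one site on one side, so at least one triggering site always lies outside the model. It is tempting to conclude that the primary estimate must be biased. It need not be: bias remains only if other sites predict the month-12 hip beyond the hip's own month-6 value, and in simulations without that feature it was zero within error. A random-intercept model pooled over arms, closer to the SAP's summary table, gave −0.01 to 0.25 with Table 2 SDs.

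Third, the larger figures could be read as bias in the primary result. They are not. The imputation column concerns a sensitivity analysis, and only if censored values are imputed that way, which the documents do not say. The SD of 9.02 belongs to the left femoral neck on zoledronic acid; placebo hip SDs run from 2.01 to 4.58. Section 14.3 uses 9.02 as a conservative value for power, so those rows are a stress case only.

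**Conclusion.** The point holds as an unreconciled conflict with a limited numerical effect. Section 10 censors by outcome, includes participants whose month-12 data are uncontaminated, and gives a different analysis set from the SAP. If it is followed, the primary total-hip estimate is diluted by about 0 to 0.2 point in the upper case with Table 2 SDs and knee sites counted, and by almost nothing if only hip sites count. The Table 2 differences are 10.4 and 15.4 points. The sensitivity imputation would be diluted by about 0.8 to 1.7 points, or at most 0.1 with hip sites only.

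The documents do not support a claim that the primary result or its significance is threatened. The sizes rest on assumed month-6 means, SDs and correlations, on distal femur values standing in for the tibia, and on everyone who reaches the cut-off declining. The number who reach it is unknown. The change should still be made, because the data are already being collected and the rule leaves the estimand undefined.

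**What to change.** Before unblinded analysis, reconcile Section 10 with the SAP:

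1. Do not censor participants who reach the cut-off but receive no further infusion. Keep their month-12 data in the primary model under the arm assigned at baseline.
2. For participants who receive the opposite treatment, state which analysis is primary: all data by randomised arm, as the SAP's intention-to-treat statement implies, or censoring from the infusion date. Report the other as supportive. Do not impute censored values around the month-6 value.
3. For the 24-month analysis, state how participants who are not re-randomised are handled and whether this includes decliners. The SAP's four groups do not place them. Keep Hypotheses 1c and 1d to re-randomised participants.
4. Report by arm how many reached the cut-off, at which sites, and how many were infused.

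The cost is one protocol sentence, a short SAP paragraph and one supportive analysis, with no new data. If post-crossover data are made primary, the estimate is diluted somewhat, and the supportive analysis shows the other view. The clinical offer itself is not questioned.

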The Research Monitor will be responsible for reviewing all safety reports generated during the study on a regular basis, and at least every 6 months. Study reports will also be reviewed on a real-time basis. The Research Monitor may ask for assistance from the biostatistician or other study personnel. After each such meeting, the Research Monitor will make a recommendation to the PI to either: 1) continue the study in its current form, 2) consider amending the protocol to include specific actions to enhance safety or safety monitoring, or 3) discontinue the protocol with provisions for orderly discontinuation in accord with good medical practice.

The Research Monitor will review on an individual basis all unanticipated problems involving risk to participants, serious adverse events, and all participant death associated with the protocol, and provide an unbiased written report of the event to the IRB. For any event determined to be an unanticipated problem involving risk to subjects or others (UPIRTSO) will be promptly reported by telephone, email, or facsimile to the HRPO. A complete written report will follow the initial notification.

The Research Monitor may discuss the research protocol with the investigators, interview human subjects, and consult with others outside of the study about the research. The Research Monitor shall have authority to stop the research protocol in progress, remove individual human subjects from the study, and take whatever steps are necessary to protect the safety and well-being of human subjects until the IRB can assess the monitor's report. The Research Monitor is responsible for promptly reporting their observations and findings to the IRB.

14. STATISTICAL PLAN and DATA ANALYSIS

14.1. Overview

Please refer to document titled, "Statistical Analysis Plan version 2.2, dated 17Jun2020," which supersedes the analysis plan described in this section.

The main goal of the analytic strategy is to determine whether active treatment versus placebo influences the trajectory of change over time in bone density. This is a clinical trial, so we

will use an endpoint analysis as the primary means to determine whether treatment has been effective. The primary dependent variable will be change in BMD from baseline. The primary dependent variable will be change in BMD from baseline. We will retain all cases in the analysis using an intent-to-treat methodology. In order to ensure that treatment efficacy is not overestimated by participants who worsen dropping out of treatment, we will use the last-observation- carried-forward (LOCF) methodology to impute any data that are missing at the end of treatment. We understand that this method has limitations and may be overly conservative, but we will also have the ability to employ growth curve modeling, which can describe change over time even when some data are missing, and when assessment timing is different across participants. We plan to study 30 participants in each group (overall $N = 60$).

14.2. Data screening

Before analyses begin, all variables will be plotted using histograms to inspect the shape of distributions and to check for outliers. Because this is a clinical trial, we will make an a priori decision to not drop cases nor transform variables. Nonetheless, these issues can be highly relevant to the accuracy of statistical inference. If we identify any possibility that our assumptions have been violated, we will employ alternative approaches to determine whether our findings still hold. As part of data screening, we will describe the amount of data that are missing, and we will compare participants with and without missing data.

14.3. Sample size determination

Determination of the sample size for this study is based on 2 factors: the data we have accumulated of BMD changes at various skeletal sites from several of our preliminary studies and from the practical issues related to the number of participants who can be recruited. Both of these approaches provide congruent results. Our preliminary DXA data from participants followed for one year after infusion of zoledronic acid and a comparable group of acute SCI participants in a parallel study who were only observed and not treated for 12 months are presented in Table 2. If one focuses simply on the total hip skeletal site, which is the primary outcome measure, the data suggest a standardized effect size of Cohen’s d of ≥ 3.9 (based on either right or left hip). This effect size would yield virtually 100% power with our planned sample size of $N = 60$. We will also, however, have enough power to detect effect sizes as small as $d = .74$ with 80% power with 30 participants within each group. Another way to express these data is to consider that the largest standard deviation in the BMD measurement at any of the hip sites was 9.02%. If we assume that this will be the standard deviation for all skeletal sites, with 30 participants/group, we will have 80% power to detect a difference of 6.5% between groups.

Region	Zoledronic Acid	Placebo
Spine	3.31 ± 2.11%	-8.04 ± 4.41%
Left Total Hip	-3.40 ± 3.51%	-13.83 ± 2.01%
Left Femoral Neck	4.60 ± 9.02%	-17.60 ± 3.42%
Right Total Hip	-2.80 ± 5.08%	-18.21 ± 2.39%
Right Femoral Neck	-1.10 ± 7.56%	-17.20 ± 4.58%
Left Distal Femur	-3.84 ± 21.99%	-26.68 ± 14.29%

Table 2: BMD changes 12 mo after SCI at various skeletal site

For the knee skeletal sites, with greater variance in measurements observed, the data support Cohen's d of ≥ 1.0 , so that with 30/group at one year, there will be 98% power to detect a change as large as is seen in our preliminary data and 80% power to detect a change as small as a 16% BMD difference between groups at BMD at a knee site. We anticipate the CT data to have much smaller variance, given our current experience from published studies, and therefore expect to be able to have adequate power to detect even smaller differences. At year 2, we will have 15 participants/group, and making the conservative assumption that the differences between treatment and placebo groups observed at one year above will not become greater after a second year, and maintaining the maximum variance, we calculate 88% power to detect a change as large or larger than seen at one year at any hip skeletal site between the treatment group (zol/zol) and the placebo group (plac/plac). There will be 80% power to identify differences between groups of 9% or more at year 2. At the knee, there will be 81% power at the end of year 2 to detect a difference as large as that observed after one year ($d = 1.0$) between the zol/zol and plac/plac groups. Therefore, a total sample size of 60 participants will permit scientifically rigorous outcomes to be achieved, and will also be clinically achievable. We do recognize that there will be some drop-outs. From our previous experience, we feel that this number will be less than 20% (our current study with 60 SCI participants has 3 who have not returned for one year visit with the remainder continuing for a second year). As data from all participants will be utilized in an ITT analysis, the drop-out rate will not directly affect sample size but will lead to lack of a greater degree of uncertainty due to need for imputation and will therefore be kept to a minimum. Even with a 20% drop-out rate, with the sample size of 60, we will have ample power to detect changes considerably smaller than those seen in our preliminary studies. Only 60 subjects will be randomized in this study, however to account for screen failures, we anticipate consenting up to 120 subjects.

15. Modifications to the Protocol

15.1. All modifications to the protocol will be handled as protocol amendments and will be submitted to the Northwestern University IRB for review. Major modifications to the protocol and any modifications that could increase risk to the participants will be submitted to the HRPO prior to implementation. Other modifications and amendments will be submitted to the HRPO at the time of the regular continuing review.

15.2. Protocol Deviations. All deviations from the protocol will be documented by the study coordinator and brought to the attention of the principal investigator. All deviations which could affect the integrity of the study and/or the safety of the participants will be reported to the Northwestern University IRB immediately and if they are UPIRTSOS to the HRPO immediately. Deviations which are minor in nature and do not affect the integrity of the study or safety of the participants (e.g., study visit occurs one week late as participant is on vacation) will be documented but not reported to the IRB. Deviations which result from misinformation due to either the participant providing it incorrectly or incompletely (e.g., concomitant medications) or failure to notice (e.g., laboratory results), will be reported to the principal investigator immediately and, if in his estimation it poses no safety threat to the participant, reported to the Research Monitor during the next DSMC meeting.

16. Reporting of Serious Adverse Events and Unanticipated Problems

The reporting of adverse events, serious adverse events and unanticipated problems will be done according to the guidelines of the Northwestern University IRB, the HRPO, and the FDA.

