3.4. Randomization Method

This study contains two randomization points – one in the beginning of the study, and a re-randomization after 12 months. For the first randomization, participants will be assigned to treatment versus placebo in blocks of 2, 4, and 6. The order of the blocks of 2, 4 and 6 will be random. Within each block of sequential participants enrolled, half will be assigned to treatment and half will be assigned to the control condition, and the order of assignment will be at random. The randomization will be determined by a predetermined list, which will be created by an unblinded study personnel using a random number generator. The remainder of the study team and the participants will remain blinded to treatment throughout the course of the study. A copy of this list will be provided in a sealed envelope to the principal investigator in the event that treatment assignment needs to be known for a participant for safety reasons.

The second randomization will determine which treatment participants receive during the second year of their participation. The goal of this second randomization is to have 50% of the treatment group be randomized to continued treatment and 50% to be switched to placebo. Within the control group, 50% will be randomized to treatment and the other 50% will receive continued placebo. To achieve this, the unblinded personnel will create a random list of treatment versus control assignment using a random number generator. Participants will be assigned to treatment versus placebo in blocks of 2 and 4. With 60 subjects planning to be randomized, up to 15 subjects will be enrolled subjects in each of the following groups: zol/zol, placebo/zol, zol/placebo, and placebo/placebo.

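### Year-2 power in Protocol 14.3 assumes 15 complete participants per group; at the protocol's own 20% drop-out bound, DXA knee power falls from 81% to 72%, so the claim of ample power fails there

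*Protocol*

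**What the plan says.** Protocol 14.3 takes 15 participants per group at year 2, assumes the one-year difference neither grows nor shrinks, and keeps the largest SD. For the knee, zol/zol against placebo/placebo, it concludes that "there will be 81% power at the end of year 2 to detect a difference as large as that observed after one year", and it prints the effect size as d = 1.0. For the year-2 hip it states 88% power.

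On losses, it expects drop-out below 20% and cites experience: "our current study with 60 SCI participants has 3 who have not returned for one year visit". Because the analysis is ITT, it says of drop-out that it "will not directly affect sample size but will lead to lack of a greater degree of uncertainty due to need for imputation" (the wording is garbled, but it evidently concedes some added uncertainty). It closes: "Even with a 20% drop-out rate, with the sample size of 60, we will have ample power to detect changes considerably smaller". The comparison there is with the changes in its preliminary data. No year, site or contrast limits that sentence.

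Two other places bear on the group size. Protocol 3.4 gives 15 as a ceiling: "up to 15 subjects will be enrolled subjects in each of the following groups". Protocol 12 says withdrawn participants will not be replaced.

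**The concern.** The year-2 power figures carry no loss, although the section itself names a loss rate and replacement is ruled out. Re-randomization has already reduced the groups from 30 to 15, and the stated knee power is only just above 80% at full size. Any loss therefore takes it below 80%, and the claim about 20% drop-out needs checking at that comparison in particular.

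Protocol 14.3 is the only power statement in the two documents; the SAP's table of contents has no sample-size section. SAP Hypothesis 1b names the zol/zol versus placebo/placebo contrast at lower-extremity sites after two years. Protocol 2.2 also projects significant year-2 knee differences, but for zol/zol versus zol/placebo and for zol/placebo versus placebo/placebo, not for the contrast behind the 81%. A reader weighing a null year-2 DXA knee result against 14.3 would think the comparison better powered than it is.

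**Working it through.** **Inputs.** From Table 2 in Protocol 14.3:
- Distal femur: -3.84 ± 21.99% on zoledronic acid and -26.68 ± 14.29% on placebo, a difference of 26.68 - 3.84 = 22.84 points.
- Left total hip: -3.40% and -13.83%, a difference of 10.43 points.
- Largest hip-site SD 9.02; largest total-hip SD 5.08.

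The section states neither alpha nor sidedness. I assume two-sided 5%; the SAP's primary analysis uses 0.05.

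**Formulas.** Normal approximation: power ≈ Φ(d·√(n/2) - 1.96), with n per group. Difference detectable with 80% power: (1.96 + 0.842)·SD·√(2/n). The t-test figures use the noncentral t with 2n - 2 degrees of freedom.

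**Reproducing the stated figures.** With the largest SD, d = 22.84/21.99 = 1.039.
- At n = 15, d·√(15/2) = 2.844 and Φ(0.884) = 81.2%, the printed 81%.
- The same method gives 98.0% for the knee at 30 per group (stated 98%) and a detectable knee difference of 15.9 points (stated 16%).
- For the year-2 hip, 10.43/9.02 at n = 15 gives 88.6% (stated 88%).
- Taken literally, d = 1.0 at n = 15 gives 78.2% (normal) or 75.3% (t), so the 81% rests on 1.04.

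**Adding loss at the year-2 knee.** At 20% loss, n = 15 × 0.8 = 12, d·√6 = 2.544 and Φ(0.584) = 72.0%.

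| Loss | n per group | Normal, d = 1.04 | t-test, d = 1.04 |
|---|---|---|---|
| 0% | 15 | 81% | 78% |
| 5% (3 of 60) | 14.25 | 79% | 76% |
| 10% | 13.5 | 77% | 74% |
| 20% | 12 | 72% | 68% |

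With d = 1.0, 12 per group gives 68.8% (normal) or 64.9% (t).

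**Detectable knee difference, SD 21.99.** At n = 15 it is 22.5 points (normal) or 23.3 (t). At n = 12 it is 25.2 or 26.3, both above the 22.84 observed. A knee difference 20% smaller than observed has 53% power at n = 12 (normal).

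**Pooled SD instead of the largest.** √((21.99² + 14.29²)/2) = 18.54, so d = 1.23. At n = 12 power is 85% (normal) or 82% (t). The detectable difference is 21.2 or 22.2 points, that is 7% or 3% below 22.84.

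**Where the sentence does hold.**
- Year 1 with 24 per group: knee power is 94 to 95%. The detectable difference is 17.8 to 18.2 points at the knee and 7.3 to 7.5 at the hip (SD 9.02).
- Year-2 hip at n = 12, 10.43 points: with SD 5.08, power stays above 99%. With the SD of 9.02 that 14.3 uses, power is 77 to 81% against the stated 88%.

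**A smaller inconsistency of method.** At 30 per group, 14.3 gives d = .74 "with 80% power with 30 participants within each group" and also says "we will have 80% power to detect a difference of 6.5% between groups". The first fits the t-test (0.736; normal 0.723), the second the normal approximation (6.52 points; t-test 6.64). The gap is small, but the section mixes two methods and names neither.

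**The case against.** The 81% is not a miscalculation: it is given for 15 per group and is correct on that basis. The drop-out sentence names no year or site and is true for most settings it could cover. The shortfall needs drop-out at a bound the protocol expects not to reach, the larger arm SD, and no information from those who leave. At the 5% loss the protocol cites, power is 79%. The SAP's mixed model uses all available observations, and DXA is repeated at months 3, 6, 12 and 18, so 72% is a completers-only figure. Most tellingly, the SAP supersedes the protocol's analysis plan and has no DXA knee endpoint; its knee endpoints are QCT, and 14.3 says "We anticipate the CT data to have much smaller variance".

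Most of this stands as a limit on the point, but it does not rescue the sentence. The 20% rate is the protocol's own condition, and so is the largest SD; relaxing the SD still leaves a detectable difference close to the observed one. The mixed model recovers some information but not a full 15 per group. No QCT variance is given, so the expected gain cannot be checked. The figures also leave out two further sources of shrinkage for which no rates are given: participants treated at month 6 are not re-randomized and their later data are censored (Protocol 10), and participants may decline the month-12 infusion (Protocol 12).

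**Conclusion.** The point holds. By the calculation behind the protocol's own 81%, year-2 DXA knee power is 72% at the protocol's 20% drop-out bound (65 to 72% across normal or t-test and d = 1.04 or 1.0). Even the full observed difference then has less than 80% power, so the claim of ample power for considerably smaller changes is wrong at that comparison.

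This rests on a two-sided 5% test, the largest Table 2 SD, an unchanged one-year difference, and drop-outs contributing nothing. With less drop-out, power lies between 72% and 81%. The finding is confined to the year-2 DXA knee: year-1 total-hip power, the year-2 total hip with its own SDs, and the SAP's QCT knee endpoints are not shown to be short of power. It should be corrected, but it does not threaten the primary result.

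**What to change.** In Protocol 14.3:

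1. Restate year-2 power for 12 to 15 per group by one named method, with alpha and sidedness. By two-sided 5% t-test with the largest SDs:
   - Knee: 68 to 78% at d = 1.04 (65 to 75% at d = 1.0); detectable difference 23 to 26 points.
   - Hip: 77 to 86% for 10.43 points with SD 9.02; detectable difference 9.6 to 10.8 points, or 5.4 to 6.1 with the total-hip SD of 5.08.
2. Except the year-2 DXA knee comparison from the sentence on power at 20% drop-out.
3. Replace the statement that drop-out does not directly affect sample size with one saying that it lowers the effective sample size and power. Keep the acknowledgement of added uncertainty.
4. State the limits: 20% is an upper bound; the largest SD is conservative (pooled SD: 82% at 12 per group by t-test); the mixed model recovers some information; and the knee figures are for DXA, not QCT.

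The cost is protocol wording and less favourable year-2 figures. No participants are added and no analysis changes.
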